APPENDIX 4: HANDLING OF BIOLOGICAL SPECIMENS

Not Applicable.

APPENDIX 5: PROTOCOL AMENDMENT 2 SUMMARY

| SAP | Statistical Analysis Plan |
| SD | Standard Deviation |
| SDC | Statistics and Data Corporation, Incorporated |
| SOC | System Organ Class |
| TEAE | Treatment-Emergent Adverse Event |
| VA | Visual Acuity |
| WHO DD | World Health Organization Drug Dictionary |

1. Introduction

The purpose of this statistical analysis plan (SAP) is to describe the planned analyses and reporting for protocol 17-100-0008, version Amendment 2.0 dated 18OCT2017.

This SAP is being written with due consideration of the recommendations outlined in the most recent International Conference on Harmonization (ICH) E9 Guideline entitled Guidance for Industry: Statistical Principles for Clinical Trials and the most recent ICH E3 Guideline, entitled Guidance for Industry: Structure and Content of Clinical Study Reports (CSR).

This SAP describes the data that will be analyzed and the subject characteristics, efficacy, and safety assessments that will be evaluated. This SAP provides details of the specific statistical methods that will be used. The statistical analysis methods presented in this document will supersede the statistical analysis methods described in the clinical protocol. If additional analyses are required to supplement the planned analyses described in this SAP they may be completed and will be identified in the CSR.

2. Study Objectives

The objective of this study is to evaluate the efficacy and safety of two concentrations of PRT-2761 (0.5% and 1%) as a topical ophthalmic solution for the treatment of the signs and symptoms of acute and chronic allergic conjunctivitis.

2.1 Primary Efficacy Measures

The primary efficacy measures are:

- Ocular itching evaluated by the subject at Visits 4b and 5a (for Duration and Onset of action, respectively) at 5(± 1), 7(± 1), and 10(± 1) minutes post-Conjunctival Allergen Challenge (CAC, 0-4 scale, allowing half-unit increments)
- Conjunctival redness evaluated by the Investigator at Visits 4b and 5a (for Duration and Onset of action, respectively) at 7(± 1), 15(± 1), and 20(± 1) minutes post-CAC (0-4 scale, allowing half-unit increments)

2.2 Secondary Efficacy Measures

The secondary efficacy measures are:

- Ocular itching evaluated by the subject at Visits 5b, 6a, 6b, and 7 at 5(± 1), 7(± 1), and 10(± 1) minutes post-CAC (0-4 scale, allowing half-unit increments)
- Conjunctival redness evaluated by the Investigator at Visits 5b, 6a, 6b, and 7 at 7(± 1), 15(± 1), and 20(± 1) minutes post-CAC (0-4 scale, allowing half-unit increments)
- Episcleral and ciliary redness evaluated by the Investigator at all dosing Visits (4b, 5a, 5b, 6a, 6b, 7) at 7(± 1), 15(± 1), and 20(± 1) minutes post-CAC (0-4 scale, allowing half-unit increments)

- Chemosis evaluated by the Investigator at all dosing Visits (4b, 5a, 5b, 6a, 6b, 7) at 7(± 1), 15(± 1), and 20(± 1) minutes post-CAC (0-4 scale, allowing half-unit increments)
- Tearing evaluated by the subject at all dosing Visits (4b, 5a, 5b, 6a, 6b, 7) at 7(± 1), 15(± 1), and 20(± 1) minutes post-CAC (0-4 scale, NOT allowing half-unit increments)
- Eyelid swelling evaluated by the subject at all dosing Visits (4b, 5a, 5b, 6a, 6b, 7) at 7(± 1), 15(± 1), and 20(± 1) minutes post-CAC (0-3 scale, NOT allowing half-unit increments)
- Rhinorrhea, nasal pruritis, ear or palate pruritis, and nasal congestion evaluated by the subject at all dosing Visits (4b, 5a, 5b, 6a, 6b, 7) at 7(± 1), 15(± 1), and 20(± 1) minutes post-CAC (0-4 scale, NOT allowing half-unit increments)

2.3 Safety Measures

The safety measures include the following:

- Slit Lamp Biomicroscopy conducted at Visits 2, 3, 4a, 4b, 5a, 5b, 6a, 6b and 7
- Dilated Ophthalmoscopy conducted at Visits 2 and 7
- Distance Visual Acuity (VA) using an Early Treatment of Diabetic Retinopathy Study (ETDRS) chart conducted at Visits 2, 3, 4a, 4b, 5a, 5b, 6a, 6b and 7
- Intraocular Pressure (IOP) Visits 2 and 7
- Adverse Events (AE) (reported, elicited, and observed) assessed at Visits 1, 2, 3, 4a, 4b, 5a, 5b, 6a, 6b and 7

2.4 Tolerability Measures

The tolerability measures include the following:

- Drop comfort assessment (0-10 unit scale) assessed by subject immediately upon instillation, at 30 seconds, and 1 minute post-instillation at Visit 4a
- Drop comfort descriptor questionnaire at 3 minutes post-instillation at Visit 4a

2.5 Exploratory Measures

The exploratory measures include the following:

- Ocular itching evaluated by the subject at Visit 5b, 6a, 6b, and 7 at 15(± 1), 20(± 1), 25(± 1) and 30(± 1) minutes post-CAC (0-4 scale, allowing half-unit increments)
- Tearing evaluated by the subject at Visits 5b, 6a, 6b, and 7 at 25(± 1) and 30(± 1) minutes post-CAC (0-4 scale, NOT allowing half-unit increments)
- Eyelid swelling evaluated by the subject at Visits 5b, 6a, 6b, and 7 at 25(± 1) and 30(± 1) minutes post-CAC (0-3 scale, NOT allowing half-unit increments)

- Rhinorrhea, nasal pruritis, ear or palate pruritis, and nasal congestion evaluated by the subject at Visits 5b, 6a, 6b, and 7 at 25(± 1) and 30(± 1) minutes post-CAC (0-4 scale, NOT allowing half-unit increments).
- Conjunctival, episcleral, and ciliary redness evaluated by the investigator at Visit 5b, 6a, 6b, and 7 at 25(± 1) and 30(± 1) minutes post-CAC (0-4 scale, allowing half-unit increments).
- Chemosis evaluated by the investigator at Visit 5b, 6a, 6b, and 7 at 25(± 1) and 30(± 1) minutes post-CAC (0-4 scale, allowing half-unit increments).
- In a subset of approximately 36 subjects who agree to undergo confocal microscopy, conjunctival inflammation as measured by confocal microscopy (0-4 scale, NOT allowing half-unit increments) at Visits 3, 4b, and 7.
- In the same subset of subjects who undergo confocal microscopy, tears will be collected from both eyes (prior to confocal microscopy) at Visit 3, 4b, and 7. At Visit 3, tears will be collected at two separate time points post-CAC: prior to the confocal microscopy procedures and again at 2 (+1) hours after instillation of the anesthetic used for the confocal microscopy procedures. At Visit 4b tears will be collected prior to the confocal microscopy procedures post-CAC. At Visit 7 tears will be collected 2 (+1) hours after instillation of the anesthetic used for the confocal microscopy procedures post-CAC. Tears will be analyzed for cytokine levels.
- Diary assessments for the subset of subjects undergoing confocal microscopy at Visits 3 and 4b. Additionally, all subjects will be dispensed diaries at Visits 5b and 6b. Assessments of ocular itching, ocular redness, and eyelid swelling will occur prior to bedtime and upon awakening (all use a 0 to 4 scale, except eyelid swelling, 0 to 3).
- In the same subset of subjects who undergo confocal microscopy, digital photographs will be taken at-home of each eye prior to subjects completing diary assessments following Visits 5b and 6b.
- Digital photographs will be taken in-office of all subjects pre-CAC and within 30 minutes of the last post-CAC assessment at Visit 4b and Visit 5a.

2.6 Statistical Hypotheses

3. Study Design and Procedures

3.1 General Study Design

This is a prospective, single-center, randomized, double-masked, vehicle and active-controlled, dose-ranging study to evaluate the efficacy and safety of PRT-2761 in two concentrations compared to Vehicle, Patanol® and Patanol®/Pred forte® for the treatment of the signs and symptoms of chronic allergic conjunctivitis.

The trial will comprise of 10 office visits over a period of up to 9 weeks. Part 1 will be a conventional CAC protocol. Subjects who meet the entry criteria for itching and redness response to the CAC at Visits 2 and 3 will be randomized at Visit 4a (Day 1, Duration of Action Visit) in a 1:1:1:1 (PRT-2761 0.5%: PRT-2761 1%: Vehicle:Patanol®) assignment ratio in the acute phase. Subjects randomized to the Patanol® treatment for the acute phase will further be randomized using a 1:1 (Patanol®: Pred forte®) assignment ratio for the chronic phase. After 8 hours, subjects will return for Visit 4b to be challenged with signs and symptoms assessed post-CAC. Subjects will return 14 days later for Visit 5a (Day 15, Onset of Action Visit), at which time they will be challenged 15 minutes after dosing with the same concentration of PRT-2761, vehicle, or Patanol® as randomized at Visit 4a. This will conclude Part 1 of the study.

Part 2 will be the assessment of chronic allergy and subjects will be challenged 15 minutes after dosing. If subjects were randomized to receive PRT-2761 0.5%, PRT-2761 1%, or vehicle at Visit 4a, subjects will continue to receive the same treatment at (Visits 5b, 6a, 6b and 7 at 8, 24, 32 and 48 hours from Visit 5a, respectively). Subjects who were randomized to receive Patanol® at Visit 4a will be further randomized into 2 groups. One group will continue to receive Patanol® through Visit 7. The other group will be dosed with Pred forte® at Visits 5b through 7. At Visit 7, final exit procedures will also be conducted and subjects will exit the study.

Study visits will be referred to in all tables and listings with the expected visit and study day corresponding to the visit to enable reviewers to understand the assessment timing without referring to the protocol visit schedule. The following table shows the scheduled study visits, their planned study day (note that there is no Day 0 and that Day 1 corresponds to the day of randomization), and the acceptable visit window for each study visit:

| Scheduled Visit | Planned Study Day | Visit Window |
|-----------------|---------------------|--------------|
| Visit 1 | Day -50 to -22 | N/A |
| Visit 2 | Day -21 | +/- 3 Days |
| Visit 3 | Day -14 | +/- 3 Days |
| Visit 4a | Day 1 | N/A |
| Visit 4b | Visit 4a + 8 hour | +1 Hour |
| Visit 5a | Day 15 | +/- 3 Days |
| Visit 5b | Visit 5a + 8 hours | +1 Hour |
| Visit 6a | Visit 5a + 24 hours | +/- 6 Hours |
| Visit 6b | Visit 6a + 8 hours | +1 Hour |
| Visit 7 | Visit 6a + 24 hours | +/- 6 Hours |

4. Study Treatments

Subjects will be assigned to one of the following treatments:

- PRT-2761 0.5%
- PRT-2761 1%
- Vehicle
- Patanol® (active reference)
- Patanol® during the acute phase / Pred forte® during the chronic phase (active reference)

4.1 Method of Assigning Subjects to Treatment Groups

All subjects screened for the study who sign an informed consent form will be assigned a 3-digit screening number that will be entered in the Screening and Enrollment Log. Screening numbers will be assigned in sequential order beginning with 001. Randomization will be used to avoid bias in the assignment of subjects to treatment and time point, to increase the likelihood that known and unknown subject attributes (e.g., demographics and baseline characteristics) are evenly balanced across treatment groups and across time points, and to enhance the validity of statistical comparisons.

Once a subject meets all qualification criteria at Visit 4a, they will be enrolled and randomly assigned to masked treatment using a 1:1:1:1 (PRT-2761 0.5%: PRT-2761 1%:Vehicle:Patanol®) assignment ratio for the acute phase. Subjects randomized to the Patanol® treatment in the acute phase will further be randomized using a 1:1 (Patanol®:Pred forte®) assignment ratio for the chronic phase. Subjects will be randomized at Visit 4a (Day 1) by assignment of the lowest 4-digit randomization number available within the appropriate stratum. Randomization will be stratified by average post-CAC itching scores [REDACTED] at baseline (Visit 3), by qualifying allergen type [REDACTED] and by confocal participation (yes and no) to ensure balance for the primary endpoint of ocular itching. The randomization numbers will start from x001, where x refers to the subject's stratum as follows:

- x = 1 for subjects in the low baseline itching, seasonal allergy, no confocal participation stratum
- x = 2 for subjects in the low baseline itching, perennial allergy, no confocal participation stratum
- x = 3 for subjects in the high baseline itching, seasonal allergy, no confocal participation stratum
- x = 4 for subjects in the high baseline itching, perennial allergy, no confocal participation stratum
- x = 5 for subjects in the low baseline itching, seasonal allergy, confocal participation stratum
- x = 6 for subjects in the low baseline itching, perennial allergy, confocal participation stratum
- x = 7 for subjects in the high baseline itching, seasonal allergy, confocal participation stratum
- x = 8 for subjects in the high baseline itching, perennial allergy, confocal participation stratum

The first 36 subjects who qualify after post-CAC assessments at Visit 3 and had tear collection at Visit 2, will be in the confocal microscopy subset. This number is estimated to ensure approximately 30

subjects in the confocal microscopy subset complete the trial. At Visit 4, these individuals will be assigned to a kit number from Stratum 5, 6, 7, or 8.

Once 36 subjects have completed confocal microscopy at Visit 3, any subjects who had tear collection at Visit 2, will not have additional tear collections or confocal microscopy. At Visit 4, these individuals will be assigned to a kit number from Stratum 1, 2, 3, or 4.

No randomization numbers will be skipped or omitted.

At Visit 4a, if a subject requires a kit from their assigned stratum, based on the above criteria, and there are no longer any kits available for that stratum, the subject will not be randomized and will be deemed a screen failure. A five-digit subject ID (two-digit site number and the three-digit screening number separated by a hyphen [i.e., nn-nnn]) will be used to identify subjects in all datasets, listings, and tables for this study.

4.2 Masking and Unmasking

When medically necessary, the Investigator may need to determine what treatment has been assigned to a subject. The Investigator will contact Ora with the details of the emergency unmasking request. Ora will make the final determination if the unmasking request will be granted. If granted, the Investigator will be permitted to use the code-break instructions available on site.

Each kit will be labeled with a two panel scratch off label. The right panel of the label, containing the scratch off portion, should be placed in the corresponding subject binder. If the Investigator determines that emergency unmasking is necessary, the Investigator should locate the subject binder containing the label and scratch off the laminate section to reveal the assigned treatment. The Investigator must also indicate in source documents and in the CRF that the mask was broken and provide the date, time, and reason for breaking the mask. Any AE or serious AE (SAE) associated with breaking the mask must be recorded and reported as specified in this protocol.

Subjects will have the investigational product (IP) treatment discontinued immediately if treatment assignment is unmasked.

5. Sample Size and Power Considerations

A large rectangular area of the page is completely blacked out with a solid black rectangle, indicating that the content has been redacted.

[REDACTED]

[REDACTED]

[REDACTED]

[REDACTED]

[REDACTED]

[REDACTED]

[REDACTED]

[REDACTED]

6. Data Preparation

All reported study data will be recorded on the electronic case report forms (eCRF) supplied by Statistics & Data Corporation (SDC) using iMedNet™. Data from source documents will be entered into the eCRF by site personnel.

After data are entered into the clinical study database, electronic edit checks and data review will be performed. All data validation specifications and procedures are detailed in the Data Validation Manual as a separate document. When the database has been declared to be complete and accurate, the database will be locked. Any changes to the database after data have been locked can only be made with the approval of the Sponsor and Ora in consultation with SDC.

All final analyses outlined in this document will be carried out after the following have occurred:

- All data management requirements are met according to SDC standard operating procedures, including data entry, performance of edit and validation checks, documentation and resolution of data queries, and database lock with written authorization provided by appropriate SDC and Sponsor personnel;
- Protocol deviations have been identified and status defined (major/minor deviations);
- Analysis populations have been determined; and
- Randomized treatment codes have been unmasked.

7. Analysis Populations

7.1 Intent-to-Treat

The Intent-to-Treat (ITT) population consists of all subjects who are randomized. All data will be included and no subjects will be excluded because of protocol violations. The ITT population will be analyzed as randomized and will be used for the efficacy analyses.

7.2 Per Protocol

The Per Protocol (PP) population is a subset of the ITT population and includes the subjects who completed the study through Visit 5a (Day 15) with no major protocol violations. This population will be analyzed as treated using observed data only for confirmatory analyses.

7.3 Safety

The safety population includes all randomized subjects who received at least one dose of investigational treatment. The safety population will be analyzed as treated and will be used for the safety analyses. No data will be excluded for any reason.

8. General Statistical Considerations

8.1 Unit of Analysis

The subject will be considered the unit of analysis for all variables with exceptions of slit-lamp biomicroscopy and dilated fundoscopy examination. For the variables using subject as the unit of the analysis, the average of both eyes of each subject will be used for statistical summaries and analyses in cases where data are collected for each eye. For slit-lamp biomicroscopy and dilated fundoscopy examination results, the eye will be the unit of analysis and summaries will be provided for all eyes combined.

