11 ADVERSE EVENTS

An AE is defined as any untoward medical occurrence associated with the use of an investigational product (IP) in humans, whether or not considered IP-related. An AE can be any unfavorable and unintended sign (eg, an abnormal laboratory finding), symptom, or disease temporally associated with the use of an IP, without any judgment about

causality. An AE can arise from any use of the IP (eg, off-label use, use in combination with another drug or medical device) and from any route of administration, formulation, or dose, including an overdose. An AE can arise from any delivery, implantation, or use of a medical device, including medical device failure, subject characteristics that may impact medical device performance (eg, anatomical limitations), and therapeutic parameters (eg, energy applied, sizing, dose release) associated with medical device.

All AEs spontaneously reported by the subject and/or in response to an open question from study personnel or revealed by observation, physical examination or other diagnostic procedures will be recorded in the source document and on the appropriate pages of the CRF. Any clinically relevant deterioration in clinical finding is considered an AE and must be recorded. When possible, signs and symptoms indicating a common underlying pathology should be noted as 1 comprehensive event.

Collection of AEs/SAEs will begin at the time of informed consent.

Documentation regarding the AE should be made as to the nature, date of onset, end date, severity, relationship to IP, action(s) taken, seriousness, and outcome of any sign or symptom observed by the physician or reported by the subject upon indirect questioning.

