14.4 Visual Acuity

Visual acuity will be assessed using an ETDRS at Visits 2, 3, 4a, 4b, 5a, 5b, 6a, 6b, and 7 prior to the CAC. For Visit 7, it will be measured again post-CAC.

VA for each eye will be calculated as the last line in which a letter is read correctly. To this value will be added the number “N x 0.02” where “N” represents the total number of letters missed up to and included in the last line read. This total sum represents the logarithm of the minimum angle of resolution (logMAR) VA for that eye.

For Example: Subject correctly reads four (4) of five (5) letters on the 0.2 line, and two (2) of five (5) letters on the 0.1 line.

| | |
|------------------------------------------------------------------|--------------|
| Base logMAR | = 0.1 |
| N (total number of letters incorrect on line 0.2 as well as 0.1) | = 4 |
| N x T (T=0.2) | = 0.08 |
| Base logMAR + (N x T) | = 0.1 + 0.08 |
| logMAR VA | = 0.18 |

VA in logMAR unit will be summarized by treatment using the average of both eyes for each subject with quantitative summary statistics. The number of subjects with worsening of acuity of 10 letters (0.2 logMAR) or more from Visit 2 will also be summarized with counts and percentages based on the total number of subjects in each treatment group with responses. Results for VA will be presented in a data listing.

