14.5 Intraocular Pressure

Intraocular pressure will be measured and recorded in mmHg post-CAC at Visits 2 and 7 and will be summarized with quantitative summary statistics by treatment using the average of both eyes for each subject. The number of subjects at Visit 7 with an IOP greater than or equal to 30 mmHg and with an increase of at least 10 mmHg in IOP from baseline will be summarized separately with counts and percentages. IOP will be listed for each eye at each visit.

15. Tolerability Analysis

All tolerability analyses will be conducted using the Safety population.

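### By default the SAP averages the two eyes before counting subjects over the VA and IOP safety limits, so a change in one eye can go uncounted; IOP at Visit 7 matters most

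*SAP*

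**What the plan says.** SAP 8.1 makes the subject the unit of analysis for everything except slit lamp and dilated fundoscopy. For per-eye data on the remaining variables, "the average of both eyes of each subject will be used for statistical summaries and analyses". VA is scored for each eye (SAP 14.4) and IOP is measured in each eye (Protocol 10.3.1.10), and neither is exempted.

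SAP 14.5 repeats the averaging for the descriptive statistics: IOP "will be summarized with quantitative summary statistics by treatment using the average of both eyes for each subject". Two counts follow in a separate sentence: "The number of subjects at Visit 7 with an IOP greater than or equal to 30 mmHg", and those "with an increase of at least 10 mmHg in IOP from baseline will be summarized separately with counts and percentages". SAP 14.4 has the same structure. The eye average is named for the logMAR summary, and then comes "The number of subjects with worsening of acuity of 10 letters (0.2 logMAR) or more from Visit 2 will also be summarized". None of the count sentences mentions either eye, the worse eye or the average.

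On timing, "Intraocular pressure will be measured and recorded in mmHg post-CAC at Visits 2 and 7". On individual data, "IOP will be listed for each eye at each visit". Protocol 8.2 makes a VA loss of more than 10 letters from Visit 2 an adverse event (AE). The visit procedures in Protocol 10.3.1 express this as a logMAR increase of at least 0.22. For IOP the only visible AE rule is the general one: "Any clinically relevant deterioration in clinical finding is considered an AE and must be recorded".

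**The concern.** A threshold count in a safety table is there to show individual outliers that a group mean hides. Averaging a subject's two eyes before applying the limit works against that, because a normal fellow eye dilutes an abnormal one. The documents use eye-level rules elsewhere. The IOP exclusion limits apply to either eye, the VA entry limit applies to each eye, and SAP 8.1 itself keeps slit lamp and fundoscopy at eye level.

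IOP is where this matters most. Baseline is Visit 2 and the only scheduled post-dose reading is Visit 7, so a rise missed there has no later scheduled chance to be counted. On the visible text, such a rise reaches a by-arm table only if the investigator judges it clinically relevant and records an AE. Otherwise it appears only in the by-eye listing. The Protocol synopsis says PRT-2761 has not previously been used in humans, so the by-arm pressure table should not look cleaner than the data behind it.

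**Working it through.** **Inputs from the documents.** VA limit 10 letters, stated as 0.2 logMAR, at 0.02 logMAR per letter (SAP 14.4). IOP limits 30 mmHg and a 10 mmHg rise (SAP 14.5). IOP allowed at entry 8 to 22 mmHg (Protocol 7.4, exclusion 12). Thirty subjects in each PRT-2761 arm and in the vehicle arm (Protocol 9.1.1).

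**The plan's own figure.** 10 letters × 0.02 = 0.20 logMAR, which agrees with SAP 14.4. The Protocol's AE limit of 0.22 is 11 letters (11 × 0.02), consistent with its more-than-10-letters wording.

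**Direction.** If the mean of two values is at least c, the larger value is at least c. So with both eyes measured at both visits, every subject counted by the average is also counted by the either-eye rule, but not the reverse.

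**How far one eye must move under the average.**
- IOP rise, fellow eye unchanged: x/2 ≥ 10 gives x ≥ 20 mmHg.
- VA, fellow eye unchanged: 0.02L/2 ≥ 0.20 gives L ≥ 20 letters (0.40 logMAR).
- IOP ≥ 30 with fellow eye at f: (x + f)/2 ≥ 30 gives x ≥ 60 − f. For f = 22, x ≥ 38. For f = 8, the bottom of the entry range, x ≥ 52.

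**Example.** Right/left pressures go from 18/18 to 32/20 mmHg. The Visit 7 mean is 26 and the mean rise is 26 − 18 = 8, so neither count includes the subject. Yet one eye is above 30 and has risen by 32 − 18 = 14.

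**Illustrative size, on assumed inputs.** The documents give no SD or between-eye correlation. Take per-eye changes as bivariate normal with common SD s and correlation r. The mean change of the two eyes then has SD s√((1 + r)/2).
- One eye truly up 15 mmHg and the fellow eye unchanged, s from 2 to 4 mmHg, r from 0 to 0.8. The average rule counts the subject with probability P(Z ≥ (10 − 7.5)/(s√((1 + r)/2))), which runs from 4% (s = 2, r = 0) to 26% (s = 4, r = 0.8). The either-eye rule counts the subject at least 89% of the time.
- The same, with both eyes truly up 15: the average rule counts 91% to over 99.9%.
- Both eyes truly up 5, s = 4, r = 0.8: average 9.4%, either eye 15.1%. In an arm of 30 that is 2.8 against 4.5 subjects.

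**Chance flags in stable subjects (true change zero), same model.**

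| Count | Assumed SD | Average (r = 0 to 0.8) | Either eye (r = 0; r = 0.8) |
|---|---|---|---|
| IOP rise ≥ 10 mmHg | 4 mmHg | 0.02% to 0.4% | 1.2%; 1.0% |
| VA ≥ 0.20 logMAR worse, per test | 0.10 logMAR | 0.2% to 1.8% | 4.5%; 3.6% |

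For example, either eye for IOP at r = 0: 1 − (1 − P(Z ≥ 2.5))² = 1 − (1 − 0.0062)² = 0.012. At SD 2 mmHg the either-eye figure is below 0.001%.

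**The case against.** The best counter-argument is textual. In SAP 14.4 and 14.5 the averaging phrase is attached to the descriptive statistics and the counts stand in separate sentences without it. If 8.1 settled everything, the repetition would be unnecessary, so a programmer might take the counts as not averaged. An either-eye count also still has the subject as its unit. This stands in part: the wording leaves room. But the averaging sentence in 8.1 covers summaries of per-eye data generally, and nothing in 14.4 or 14.5 displaces it. If either eye is what the sponsor intends, the SAP still has to say so.

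Three stronger readings are tempting, and the documents do not support them.
- *IOP has no numeric AE trigger.* A reader might infer this because none is visible. Protocol Appendix 2, on examination procedures, is redacted, so one there cannot be excluded.
- *The averaged count can never exceed the either-eye count.* This needs both eyes at both visits, and the missing-data rules in SAP 8.2 are redacted. Suppose baseline is 10/22 (mean 16), only the second eye is read at Visit 7, at 26, and the available eye is used. The computed rise is 10 and the subject is counted, though that eye rose 26 − 22 = 4.
- *The VA counts would be pooled over visits.* SAP 8.4 already provides for summaries by visit where appropriate.

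It is also fair to say that the practical weight is limited. Both eyes are dosed (Protocol 9.1.2), so similar responses in the two eyes are plausible and would narrow the gap. IOP is listed by eye, and clinically relevant deterioration must be recorded as an AE. For VA the numeric AE rule covers most of what the average would miss. A one-eye loss of exactly 10 letters, with the fellow eye unchanged, falls below the AE limit and is also missed by the averaged count.

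**Conclusion.** The point holds as a default that can under-count. As written, SAP 8.1 leads to averaging the eyes before the VA and IOP limits are applied, and 14.4 and 14.5 give no other rule. The exact part rests only on the documents' figures and on both eyes being measured at both visits. With an unchanged fellow eye, the one-eye change needed is doubled, to 20 mmHg or 20 letters. With the fellow eye at 22 mmHg, the IOP needed for the 30 mmHg count is 38. The size of the under-count in this trial is unknown. The probabilities above depend on assumed SDs, correlations and true rises, and serve only to show the range.

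IOP at Visit 7 is the main gap, subject to the redaction of Appendix 2; the VA gap is small. A reader might infer that one-eye events would be lost or that the efficacy conclusions are affected. Neither follows. The eye-level IOP data are kept and listed, Protocol 12.14 treats VA and IOP as descriptive secondary safety variables, and no test or success rule uses these counts. The SAP should be corrected because the by-arm safety table can look better than the by-eye data, and the remedy is cheap.

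**What to change.** In SAP 8.1, add the VA and IOP threshold counts to the exceptions from averaging. In 14.4 and 14.5, state that a subject is counted when either eye meets the criterion, with change computed within eye against that eye's own reference value. Keep the two-eye average for the descriptive means.

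The cost is a few words of text and a few lines of code. No new data are needed, since VA is calculated and IOP recorded for each eye. The downside is slightly more chance flags: on the assumed SDs, at most about 1.2% per subject for an IOP rise of 10 mmHg or more (SD 4 mmHg), and about 4.5% per VA test (SD 0.10 logMAR). The vehicle arm, counted by the same rule, gives the background rate against which to read them.
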